- The subject is currently using Tretinoin and topical retinoids, e.g., Retin-A®, Renova® and exfoliating products. Although use in the area to be treated is not absolutely contraindicated, it is known to make skin more sensitive and prone to exfoliation. Candidates for Icon™ treatment should be advised to discontinue the use of exfoliating creams and other exfoliating products two (2) weeks prior to and during the entire treatment course.
- The subject has a history of heat urticaria. They may develop hives with exposure to light pulses.
- The subject has Herpes I or II within the treatment area. Before a treatment, candidates should consult their primary care physician for medical evaluation and possible prophylaxis to minimize the chance of a herpetic breakout. A small percentage of persons may experience an activation of oral herpes simplex virus infection within 5-10 days after the procedure, even with appropriate prophylaxis.
- The subject has received Botulinum treatments in the treatment area. There is the possibility for increased diffusion of Botulinum, such as Botox®, as a result of edema associated with facial light-based treatment, which may result in facial asymmetry when these procedures are performed at the same visit. Many physicians recommend waiting for a minimum of 2 weeks after a Botox injection before performing facial light-based treatments. Cynosure has conducted no clinical trials and cannot recommend any specific waiting time.
- The subject has Pigmented Lesions in treatment area. If treating over a pigmented lesion, the lesion must be diagnosed as benign by a qualified practitioner prior to treatment. Inaccurate diagnosis and inadvertent treatment of a skin cancer may lead to a delay in the person receiving proper medical care.
- The subject has Cosmetic Dermal Fillers/Implants in treatment area. This Handpiece has not been evaluated or tested on areas with cosmetic dermal fillers, neurotoxins, or implants.
- The subject has had unprotected sun exposure or use of tanning beds or creams in areas to be treated. Protected sun exposure means wearing protective clothing and the daily use of a SPF-45 or greater sunscreen. Those being treated should be advised to discontinue indoor and outdoor tanning at least four (4) weeks prior to treatment, during the treatment course, and four to six (4 to 6) weeks after treatment. This will reduce the chance of skin color changes and manifestation of new pigmented lesions.

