2.8 Post Treatment Procedures

- Adverse events will be documented after treatment.
- Photographs may be taken post treatment.
- After treatment 1 only, subjects will be asked to complete a Post Treatment 1 Questionnaire.
- The following post treatment instructions will be reviewed:
 - If the skin is slightly pink or red in areas following the treatment, avoid hot water when washing or showering until any erythema (redness) has subsided.
 - Soothing creams or moisturizers, such as Aveeno, may be used.
 - Gently massage the treated area daily for 5 minutes for the duration of your involvement in the study.
 - Use a sun block with UVA and UVB protection with SPF of 30 or greater to prevent sun damage.
 - Maintain the same weight and exercise routine throughout the study.
- If the subject is treated with the Icon device, the following post treatment instructions will also be reviewed:
 - A mild sunburn-like sensation is expected. This usually lasts two to twenty-four (2-24) hours but can persist up to seventy-two (72) hours. Mild swelling and/or redness may accompany this, but it usually resolves in two to three (2-3) days. Apply wrapped ice or gel packs to the treatment area for ten to fifteen (10-15) minutes every hour for the next four hours, as needed. Never apply ice directly to skin. An oral, over-the-counter anti-inflammatory (ibuprofen such as Advil®) or an analgesic (acetaminophen such as Tylenol®) may be taken to reduce discomfort. Use medicine according to manufacturer's recommendations.
 - Until redness has resolved, it is recommended to avoid the following:
 - Applying cosmetics to treated areas.
 - Swimming, especially in pools with chemicals, such as chlorine.
 - Hot tubs, Jacuzzis, and saunas.
 - Activities that cause excessive perspiration or any activity that may raise core body temperature.
 - Sun exposure and tanning in treated areas. Apply a SPF 45 or greater sunscreen to prevent skin color changes.
 - Aggressive scrubbing and use of exfoliants on the treated area.
 - Bathe or shower as usual. Treated areas may be temperature-sensitive.

- Pigmented lesions may initially look raised and/or darker with a reddened perimeter.
- Pigmented lesions will gradually turn darker over the next twenty-four to forty-eight (24-48) hours. It may turn dark brown or even black.
- Pigmented lesions will progress to darkening and/or crusting and will start flaking off in an average of seven to twenty-one (7-21) days.

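### Icon aftercare in section 2.8 ties tanning and exfoliant avoidance to redness (usually 2-3 days), while section 2.3 advises longer periods; the two should be aligned

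*Combined protocol and SAP*

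**What the plan says.** Section 2.3, under the additional cautionary criteria for Icon, gives two precautions with durations.

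- **Tanning.** The advice for subjects under treatment is this: "discontinue indoor and outdoor tanning at least four (4) weeks prior to treatment, during the treatment course, and four to six (4 to 6", where the last range is in weeks after treatment. The reason follows: "This will reduce the chance of skin color changes and manifestation of new pigmented lesions".
- **Exfoliants.** The advice for candidates is this: "discontinue the use of exfoliating creams and other exfoliating products two (2) weeks prior to and during the entire treatment course". The same item notes that "use in the area to be treated is not absolutely contraindicated".

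Section 2.8 covers what is gone through with the subject after a session: "If the subject is treated with the Icon device, the following post treatment instructions will also be reviewed". One of those instructions is a list introduced by "Until redness has resolved, it is recommended to avoid the following". Sun exposure and tanning of the treated area are on it, and so are hard scrubbing and exfoliants. Of swelling and redness, section 2.8 says that "it usually resolves in two to three (2-3) days". It neither repeats the section 2.3 periods nor refers back to them.

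Section 2.8 also has sunscreen advice: SPF 30 or greater for all subjects with no end date, and an SPF 45 or greater sentence attached to the Icon tanning item.

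**The concern.** The same two precautions have two different stopping points in one protocol. The shorter one is in the text that staff review with the subject after treatment; the longer one is in the subject selection criteria. A Group B subject who is told to avoid tanning until the redness goes could reasonably take that as the whole restriction.

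What is at stake is safety. The sponsor gives pigment change and new lesions as the reason for the longer tanning window, and section 2.14 lists skin burns, hypopigmentation and hyperpigmentation as possible Icon effects. Group B is made up of subjects who present with pigmented or vascular lesions (section 2.1), and the face is the treated area. Nothing statistical depends on this.

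**Working it through.** The plan gives no figure to reproduce. The check sets the two sections side by side and counts days.

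**Inputs**

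- Tanning advice after treatment, section 2.3: 4-6 weeks, so 4 × 7 = 28 to 6 × 7 = 42 days.
- Exfoliant advice, section 2.3: the entire course, with no period stated after it.
- Limit on both in section 2.8: resolution of redness, usually 2-3 days.
- Spacing of Treatments 1-4, section 2.12: 1-2 weeks, so 7-14 days.
- Icon sessions in Group B, section 2.1: two of the four treatments, in no fixed order.

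**Assumptions.** The course runs from the first to the last Icon session, and the after-treatment window starts at the last one. Redness lasts the usual 2-3 days; each further day of redness shortens the differences below by one day.

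**Is tanning really on the redness-limited list?** Indentation is lost in the extracted text. However, the tanning item stands between other things to avoid (before it, activities that raise body temperature; after it, scrubbing and exfoliants) and ahead of the bathing advice. It therefore belongs to the list.

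**After the last Icon session, tanning.** Difference = section 2.3 period minus section 2.8 period.

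- Smallest: 28 − 3 = 25 days.
- Largest: 42 − 2 = 40 days.

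**Between Icon sessions at adjacent visits, tanning and exfoliants.** Difference = gap between visits minus section 2.8 period.

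- Smallest: 7 − 3 = 4 days.
- Largest: 14 − 2 = 12 days.

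If TempSure-only visits fall between the two Icon sessions, the interval is longer; it is the same gap in wording, not a further one. For exfoliants there is no difference to count after the course, because section 2.3 sets no period there.

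**The case against.** The strongest reply is that the sections do not contradict each other. Section 2.3 is operative and says what subjects should be advised. Section 2.8 does not say that anything may resume, and a site can follow both by applying the stricter rule. The redness list can also be read as a separate acute-phase precaution: it sits with cosmetics, chlorine and hot tubs, and it is stricter than section 2.3 in discouraging sun exposure altogether. On exfoliants, section 2.3 is itself only cautionary. Most of this stands, and it keeps the point small. It does not remove the point, because section 2.8 states its own, shorter limit and does not point to the longer one.

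There are also safeguards. Section 2.7 requires test spots before Icon treatment and allows a melanin reading. A subject who had tanned between sessions would meet those checks before the next one. They do nothing for the weeks after the last session.

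A reader might infer four stronger things that the documents do not support:

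- **That section 2.8 permits tanning or exfoliants once redness clears.** It is silent on resumption.
- **That sun protection drops to SPF 30 at that point.** The SPF 45 sentence is a positive instruction, and its stated purpose, preventing skin colour change, is not tied to redness. It need not lapse with the list.
- **That subjects receive only the section 2.8 wording.** Sections 2.4 and 2.5 have pre and post treatment instructions reviewed at screening and before consent, and section 7.0 lists a separate sheet. That sheet is not among the documents, so it may carry the section 2.3 periods.
- **That section 2.6 needs the Icon lead-in periods and a rule putting TempSure-only sessions first.** This would touch only a subject still tanning or using the products at a screening visit held on the day of Treatment 1, and section 2.4 already has medication discontinuation discussed. Treatment 3 falls at 2 × 7 = 14 to 2 × 14 = 28 days, so the ordering would meet the 28-day tanning lead-in only with both gaps at their maximum.

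**Conclusion.** The point holds as a minor safety-wording correction. For the same Icon precautions, section 2.8 gives subjects an earlier stopping point than section 2.3 does: about 25-40 days earlier for tanning after the last Icon session, and about 4-12 days before the next session for tanning and exfoliants when Icon is given at adjacent visits.

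These figures measure a difference between two texts. They are not days on which a subject is known to be unprotected. They rest on the usual redness duration and on the stated reading of the course; reading the course as all four treatments could only lengthen the restricted period. Whether subjects would in practice hear the longer periods turns on the unseen instruction sheet. Only Group B is affected, and no endpoint, sample size or analysis changes.

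**What to change.** In section 2.8:

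- Take tanning and exfoliants out of the redness-limited list and give them their own lines with the section 2.3 durations: no tanning through the course and for 4-6 weeks after the last Icon session; no exfoliating products through the course, including any optional fifth Icon treatment.
- Make clear that SPF 45 or greater with protective clothing applies for the same period as the tanning advice. This matches the section 2.3 definition: "Protected sun exposure means wearing protective clothing and the daily use of a SPF-45 or greater sunscreen".
- Leave the other acute-phase items where they are.

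Then check the subject's pre and post treatment instruction sheet and bring it into line.

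The cost is a wording amendment with IRB approval. The downside is a longer explicit restriction for Group B subjects, though one that section 2.3 already advises. Visit windows stay as they are.

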2.4 Screening

Subjects will be asked questions about their medical history, may have a limited physical and their inclusion/exclusion criteria will be verified. Discontinuation of any concomitant medications will be discussed, and pretreatment instructions and post treatment instruction will be reviewed with the subject.

Procedure for the Limited Physical Exam:

If the investigator determines that a limited exam is necessary, the exam will be like a basic annual physical exam performed by a primary care doctor to determine general overall health. The limited medical exam may include all or any of the following; vital signs such as blood pressure, heart rate, respiratory rate and body temperature, general appearance, listening to the heart, lungs and abdomen with a stethoscope, head and neck exam, in addition to examining the throat, tonsils, teeth, ears, eyes and nose as well as a neurological exam such as testing muscle strength, reflexes, balance, sensory changes of the extremities and mental state.

2.5 Informed Consent Process and Enrollment

Subjects will be asked to review the pre and post treatment instructions prior to signing the informed consent form and their involvement in the study. Subjects will be informed of site's COVID-19 procedures that adhere to federal and state guidelines at this time. Subjects who sign the informed consent will be screened to confirm eligibility and, if eligible, will be assigned a subject identification number. Subjects will be de-identified through their subject identification number, which will be stored in a secure location. Subject identification numbers will be generated chronologically and assigned only to subjects who have met all the study selection criteria and have signed the informed consent form. The informed consent will be obtained prior to a subject's involvement in any study related procedures. A subject will be considered enrolled in the study once they have signed the informed consent form.

2.6 Pre-Treatment Procedures

If the subject is of childbearing potential (i.e. females not post-menopausal or not surgically sterile), they will be asked if they are pregnant, the date of their last menstrual cycle, and perform a urine pregnancy test at the site prior to their first treatment. Pregnancy verification will be performed by verifying the date of their last menstrual cycle at each subsequent treatment. A urine pregnancy test may also be conducted at the Investigator's discretion at any time during the study. If a urine pregnancy test is conducted, then a negative result must be obtained within 24 hours prior to the treatment.

Urine Pregnancy Test Procedure:

1. A urine sample is tested mid-stream or by cup sample with an indicator stick.
 2. Negative results are indicated on the indicator stick.
- Photographs will be taken prior to the first treatment and may be taken prior to each subsequent treatment.
 - The following Pre-Treatment instructions will be reviewed:
 - Shave any visible hair on the area to be treated.
 - Do not wear constrictive clothing. Your back must be accessible for the neutral pad to be attached.
 - The treatment area must be free of any open lesions or infections.
 - For an optimum treatment, keep hydrated by drinking water (at least 8 cups daily) or hydrating fluids, such as Gatorade, and avoid drinking alcohol for 24 hours in advance.

2.7 Treatment Procedures

- Prior to treatment 1 only, subjects will be asked to complete a Pre-Treatment 1 Questionnaire.
- The defined study area will be identified and may be marked with a surgical marker.
- Procedures for the TempSure treatment:
 - A neutral pad will be placed on the back in an area determined by the Investigator to maintain standard energy settings and to require less power from the device during the treatment.
 - The subject may be required to wear eye shields at the discretion of the Investigator.
 - Gel will be applied to the treatment area.
 - The handpiece will be placed in contact with the skin.
 - The entire defined treatment area will then be treated by delivering energy to the skin.
 - Temperature will be continuously monitored and recorded during treatment.
- Procedures for the Icon treatment:
 - All operators and subjects will wear appropriate protective eyeglasses during the pulse-light treatments.
 - The Skintel Melanin Reader may be used for objective measurement of the melanin content of skin. The Skintel Reader may provide guidance to help select test spot settings.
 - Test spots will be performed prior to treatment in an area in or close to the treatment area in order to determine safe parameters for treatment.
 - The handpiece will be placed in contact with the skin.
 - The entire defined treatment area will then be treated by delivering adjacent pulses with minimal overlap of 20% or less.

- An air-cooling system may be used during treatment. The air-cooling system allows for the continuous flow of cold air on the treatment area to ease the sensation from the pulse.
- Parameters may be adjusted throughout the treatment to increase subject comfort.
- Subjects will be asked to report the general level of treatment discomfort/pain on a scale of 0 (none) to 10 (maximum intolerable pain).
- Photographs may be taken during treatment.
- The additional treatments will follow the same procedure.
- Subjects will receive up to 4 treatments on the face. Subjects in group B may be asked to return for an optional 5th treatment with the Icon device (and/or TempSure device) at the discretion of the Investigator.

2.8 Post Treatment Procedures

- Adverse events will be documented after treatment.
- Photographs may be taken post treatment.
- After treatment 1 only, subjects will be asked to complete a Post Treatment 1 Questionnaire.
- The following post treatment instructions will be reviewed:
 - If the skin is slightly pink or red in areas following the treatment, avoid hot water when washing or showering until any erythema (redness) has subsided.
 - Soothing creams or moisturizers, such as Aveeno, may be used.
 - Gently massage the treated area daily for 5 minutes for the duration of your involvement in the study.
 - Use a sun block with UVA and UVB protection with SPF of 30 or greater to prevent sun damage.
 - Maintain the same weight and exercise routine throughout the study.
- If the subject is treated with the Icon device, the following post treatment instructions will also be reviewed:
 - A mild sunburn-like sensation is expected. This usually lasts two to twenty-four (2-24) hours but can persist up to seventy-two (72) hours. Mild swelling and/or redness may accompany this, but it usually resolves in two to three (2-3) days. Apply wrapped ice or gel packs to the treatment area for ten to fifteen (10-15) minutes every hour for the next four hours, as needed. Never apply ice directly to skin. An oral, over-the-counter anti-inflammatory (ibuprofen such as Advil®) or an analgesic (acetaminophen such as Tylenol®) may be taken to reduce discomfort. Use medicine according to manufacturer's recommendations.
 - Until redness has resolved, it is recommended to avoid the following:
 - Applying cosmetics to treated areas.
 - Swimming, especially in pools with chemicals, such as chlorine.
 - Hot tubs, Jacuzzis, and saunas.
 - Activities that cause excessive perspiration or any activity that may raise core body temperature.
 - Sun exposure and tanning in treated areas. Apply a SPF 45 or greater sunscreen to prevent skin color changes.
 - Aggressive scrubbing and use of exfoliants on the treated area.
 - Bathe or shower as usual. Treated areas may be temperature-sensitive.

- Pigmented lesions may initially look raised and/or darker with a reddened perimeter.
- Pigmented lesions will gradually turn darker over the next twenty-four to forty-eight (24-48) hours. It may turn dark brown or even black.
- Pigmented lesions will progress to darkening and/or crusting and will start flaking off in an average of seven to twenty-one (7-21) days.
- Vascular lesions may undergo immediate graying or blanching, or they may exhibit a slight purple or red color change. The vessels will fully or partially fade in about ten to fourteen (10-14) days.
- Do not pick or pull at darkened lesions as scarring may occur.

2.9 Follow Up

- Subjects may receive a phone call 1 week (1-7 days) after each treatment to record side effects.
- Subjects will return for follow up visits at 4 and 12 weeks post last treatment.
- Photographs will be taken, adverse events will be documented, and subject questionnaires will be performed at all follow up visits.
- Any subject affected by COVID-19 that is not able to attend their follow up visits to complete the study will be asked to return to the site for a final follow up visit within 1 year of last treatment.
- Some subjects may have an incomplete response or no response by the end of the study. At the end of the study, treatments using an FDA approved/cleared treatment method may be discussed with the subject and obtained at the cost of the subject.

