2.12 Schedule of Visits and Procedures

	Visit #1*	Visit #2 - 5	Treatment Visit*** (Optional)	Call (Optional)	Visit #6	Visit #7
Procedure	Screening and Pretreatment Procedures	Treatment Visits 1-4 (1 - 2 weeks apart)	Treatment Visit #5 (2 - 3 weeks post last treatment)	Phone Call 1 Week Post Each Tx (1-7 Days)	Follow Up 4 Weeks Post Last Tx (+/- 1 Week)	Follow Up 12 Weeks Post Last Tx (+/- 1 Week)
Medical History	X					
Pregnancy Verification**	X	X	X			
Informed Consent	X					
Photographs	X	X	X		X	X
FWSS	X				X	X
Subject Pre-Treatment 1 Questionnaire		X				
Treatment		X	X			
Treatment Discomfort/ Pain Evaluation		X	X			
Subject Post Treatment 1 Questionnaire		X				
PGAIS					X	X
SGAIS					X	X
Subject Follow Up Questionnaire					X	X
Adverse Events Assessment	X	X	X	X	X	X

*Screening and Pretreatment Procedures may occur at the same time as the first Treatment Visit.

**Pregnancy verification required before each treatment only for women of childbearing potential.

***Group B only

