2.14 Adverse Event Recording

All data captured must be supported by the Investigator’s timely assessment and documentation of the adverse event in the case report forms or source documents. All documented adverse events will be reviewed by the Sponsor or designee to determine whether the adverse event meets regulatory reporting requirements and to ensure timely adverse event reporting to meet local and global regulatory requirements. All adverse events must be followed until their resolution.

Adverse Events Pertaining to the TempSure Device:

Mild discomfort during treatment may be experienced by the subject. Typically, the discomfort is temporary and localized within the treatment area. Mild edema (swelling) and erythema (redness) may occur. Initial studies indicate that these side effects typically resolve within 2 to 24 hours.

Other anticipated side effects may include; pain, skin burns, bleeding, scarring, crusting, bruising, infection, itching, prolonged edema (swelling) and erythema (redness), hardness, and nodules. Loss of hair pigment may also occur within and adjacent to the treatment area.

Adverse Events Pertaining to the Icon Device:

Adverse effects can include discomfort/pain, redness, swelling, pinpoint bleeding, skin peeling, itching, scabbing, crusting, purpura, and bruising, which are usually transient and resolve without intervention.

Possible adverse effects include pustules (such as ingrown hairs), skin burns, hypopigmentation, hyperpigmentation, removal or lightening of freckles, scarring, infection and allergic reaction (such as a rash). There is also risk of incidental hair reduction or removal in the treated areas.

People of Middle Eastern and Mediterranean descent and those who have an ill-defined hair line with no obvious transition of the hairline to the face are at a high risk for hair stimulation (paradoxical hair growth).

Adverse Events Pertaining to Gel:

The gel is a water-based gel that may be placed on the skin during the TempSure® treatment. No known adverse events are documented. However, an allergic reaction is always possible when placing a topical gel onto the skin. Allergic reaction may include a mild reaction such as skin redness, irritation, or hives.

Adverse Events Pertaining to Neutral Pad:

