2.15.6 Analysis of Safety Variables

Safety will be assessed through the degree of pain/discomfort related to the procedure (universal pain scale) and the collection of Adverse Events throughout the course of the study. For each treatment group these variables will be summarized. The summaries will include the number and percent of patients for each outcome. No statistical comparisons will be performed for any of these variables.

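### The post-treatment safety call is optional with no rule on who is called, so recording of events that start or persist after the subject leaves is uneven, most of all after the last session

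*Combined protocol and SAP*

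**What the plan says.** **The call.** Section 2.9: "Subjects may receive a phone call 1 week (1-7 days) after each treatment to record side effects". Section 2.1 uses the same permissive wording, and the schedule in 2.12 heads the call column as optional. No section says which subjects are called, what they are asked, or that completion of the call is recorded.

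**Required collection.** Section 2.8: "Adverse events will be documented after treatment". The schedule in 2.12 marks an adverse event assessment at every treatment visit and at both follow-up visits. Section 14.0 tells subjects that they may contact the investigator at any time, and 2.10 allows unscheduled visits.

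**How long effects last.** For mild discomfort, edema and erythema from TempSure, 2.14 says: "Initial studies indicate that these side effects typically resolve within 2 to 24 hours". It then lists other events outside that statement: "Other anticipated side effects may include; pain, skin burns, bleeding, scarring, crusting, bruising, infection, itching, prolonged edema (swelling) and erythema (redness), hardness, and nodules". For the sunburn-like sensation after Icon, 2.8 says: "This usually lasts two to twenty-four (2-24) hours but can persist up to seventy-two (72) hours". The same section puts Icon swelling or redness at two to three days.

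**Timing of later visits.** In 2.12, sessions 1–4 are 1–2 weeks apart, and the optional fifth (Group B) is 2–3 weeks after the previous one. The first follow-up column reads "Follow Up 4 Weeks Post Last Tx (+/- 1 Week".

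**Reporting.** Section 2.15.6 summarises safety by treatment group: "The summaries will include the number and percent of patients for each outcome". It does not mention call status.

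**The concern.** Collection of adverse events is a safety objective (1.2), and a side effect profile acceptable to the physician is one of the success conditions in 2.15.1. Section 3.3 says the study uses a handpiece not yet cleared, and 3.2 allows that some side effects may be unknown.

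A same-day check cannot record what appears after the subject goes home, nor how long an effect lasts. The protocol expects both to matter. Section 2.14 lists peeling, scabbing, crusting and bruising after Icon, usually transient, and it separates prolonged edema and erythema from the ordinary short-lived kind. It also requires every event to be followed to resolution, yet the only contact scheduled in the days when most effects would resolve is one that a site may skip.

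If three sites use the option differently, a lower recorded rate at one site or in one group could reflect fewer calls rather than fewer events, and the summary would not show it.

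**Working it through.** The plan states no event rate, call coverage, detection probability or precision target, so there is no figure of its own to reproduce. Two things can be checked: the contact gaps, which follow from the schedule, and how far the size of any loss depends on assumptions.

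**Step 1. Gaps to the next required contact if no call is made (from 2.12)**

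| After | Calculation | Gap |
|---|---|---|
| Sessions 1–3 | 1–2 weeks | 7–14 days |
| Session 4, when a fifth follows | 2–3 weeks | 14–21 days |
| Last session | 28 ± 7 days | 21–35 days |

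The last gap is 21/14 = 1.5 to 35/7 = 5 times the gap after sessions 1–3. Under 2.9, a subject kept from follow-up by COVID-19 may be seen only at a final visit within a year of the last treatment.

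**Step 2. Compare with the stated durations.** Mild TempSure effects last up to 24 hours (1 day), Icon sensation up to 72 hours (3 days), and Icon swelling or redness 2–3 days. The shortest gap, 7 days, exceeds all of them. Without a call, an effect of this kind that was not recorded on the treatment day reaches the record only by later recall or by the subject's own report. So does the end date of one that was.

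**Step 3. Illustration of size.** Let

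recorded rate = q × [s + (1 − s) × (f × dc + (1 − f) × dn)]

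where q is the true per-session event rate, s the share seen at the same-day check, f the share of subjects called, and dc and dn the detection of the remaining events with and without a call. All values are assumptions, none from the documents: q = 20%, dc = 0.9, dn = 0.7 when the next contact is at 1–2 weeks and 0.4 when it is at 3–5 weeks. Calling is taken as unrelated to having an event.

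| Same-day share s | Session | No calls | Half called | All called | Shortfall, none against all |
|---|---|---|---|---|---|
| 0 | Last | 8% | 13% | 18% | 10 points |
| 0.5 | Last | 14% | 16.5% | 19% | 5 points |
| 0.9 | Last | 18.8% | 19.3% | 19.8% | 1 point |
| 0 | 1–3 | 14% | 16% | 18% | 4 points |
| 0.5 | 1–3 | 17% | 18% | 19% | 2 points |
| 0.9 | 1–3 | 19.4% | 19.6% | 19.8% | 0.4 points |

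For example, last session with s = 0 and no calls: 0.20 × 0.4 = 8%; all called: 0.20 × 0.9 = 18%. The shortfall is q × (1 − s) × (dc − dn), so it scales with q. For q from 10% to 30%, the last-session figure runs from 5 to 15 points at s = 0 and from 0.5 to 1.5 points at s = 0.9.

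**Step 4. Effect of a mandatory call.** The longest gap from a session to a required safety contact falls from 35 days to at most 7.

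**The case against.** The strongest reply is that collection does not rest on the call. Events are documented after each treatment and at every later visit, and subjects can report at any time. The short-lived mild TempSure effects are the ones most likely to be seen on the treatment day. This stands, and it limits the point to events that begin, or continue, after the subject leaves.

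A reader might infer that the 2–24 hour statement describes side effects in general. It covers only mild TempSure discomfort, edema and erythema. Burns, scarring, nodules and other listed events fall outside it, and some could still be visible at a later visit.

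A reader might also infer that sites will call mainly subjects who had a difficult session. Nothing in the documents says so. Such calling would capture more events than the illustration shows at the same coverage, because the illustration treats calling as unrelated to events.

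The consequences have limits too. The success condition is a physician's judgement with no rate threshold, 2.15.6 plans no statistical safety comparison, and the groups are formed by presence of lesions, so their rates would not be cleanly comparable even with universal calls.

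Finally, a call on day 1–7 usually comes after a 2–24 hour effect has ended. It shortens recall rather than observing the event, and a day-7 call can coincide with the next session. That argues for a fixed early day, not for leaving the call optional. Open reporting does not close the gap either: Icon subjects are told in advance to expect sensation, swelling and redness, so they have little reason to report them.

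**Conclusion.** The point holds in this form: as written, the plan gives uneven recording of short-lived events that appear after the visit, and of how long effects last. The gaps of 7–14, 14–21 and 21–35 days come directly from the schedule, and the exposure is greatest after the last session.

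The documents do not support the stronger statement that adverse event rates *are* biased low. Missed contacts lose events rather than add them, so under-recording is the probable direction. Its size cannot be derived from the documents. Under the assumptions shown, with a true rate of 20%, calling no one after the last session costs between 1 and 10 points against calling everyone. It is small if most events are seen the same day.

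The change is worth making because it is cheap and makes the recording uniform, not because a large bias has been shown.

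**What to change.** - In 2.1, 2.9 and 2.12, change *may receive* to *will receive* for every subject after every session; at minimum, require the call after the last session.
- Set one fixed target day early in the existing 1–7 day window.
- Use a fixed checklist of the effects anticipated in 2.14, with onset and resolution dates, so that ordinary and prolonged edema or erythema can be told apart.
- Record whether each call was completed. An unreached call must not count as no event for that interval; events learned by another route still count.
- In 2.15.6, report the number of calls completed by group and by site beside the adverse event summary.

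**Cost.** 50 subjects × 4 sessions = 200 short calls by existing staff, plus one for each Group B subject who has a fifth session. The total reaches 250 only if all 50 do. No visit is added.
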